### 4 Summary

5

6 We conducted a clinical study that assessed safety and efficacy of mito-MES as post-exposure 7 prophylaxis against viral infections including RSV and SARS-CoV-2 in adults. Given extensive published data regarding safety of mito-MES in humans (presented herein) and urgent need to 8 9 develop novel oral antiviral agents, we believe that an open label exploratory safety and efficacy 10 study will obtain proof of concept data whether mito-MES has antiviral activity in humans. This is a feasibility study to determine the safety and efficacy of the treatment with mito-MES 20 mg 11 daily for up to 14 days to prevent development of severe clinical symptoms of any viral infection 12 in high-risk close household contacts of cases with viral infection. Primary efficacy measures will 13 be development of viral illness (YES/NO) throughout the study period. Secondary endpoints will 14 be new onset fever (T> 100.3 F or 38C), duration of ANY of at least three respiratory/systemic 15 symptom of viral illness in days and severity of viral illness based on a quantitative score system 16 17 within 14 days after exposure.

18

The team will post advertisements on social media seeking both individuals who have been newly diagnosed, as well as people who have recently been exposed to a suspected case of viral infection. Participants within the US who meet the inclusion criteria can enroll. The study team will also actively seek out such new cases by building referral pathways from clinics, schools, communities, Emergency Departments, inpatient units, occupational health departments, and public health authorities in the vicinity of the study site. Once the list of

1	exposed contacts for each case is identified, the study team will make multiple attempts to
2	contact them for up to 24 h, in order to obtain their decision about trial participation.
3	Enrollment of exposed persons will typically occur by first identifying suspected respiratory viral
4	infection, and then conducting contact tracing to define a ring of exposed contacts around those
5	index cases.
6	
7	Title of Study.
8	
9	An Open Label Feasibility study in adults to test the safety and efficacy of
10	mitoquinone/mitoquinol mesylate as prophylaxis for development of severe viral illness
11	
12	Investigators/Study Center:
13	
14	Name and address and statement of the qualifications of investigator
15	
16	[name], PhD, Msc University of California, Los Angeles
17	Med-Infec Dis

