18	[name]
19	
20	For qualifications see attached curriculum vitae
21	
22	Name and address of the research facilities to be used
23	
24	[name], PhD, Msc University of California, Los Angeles

1	Med-Infec Dis
2	[name]
3	
4	Name and address of reviewing Institutional Review Board
5	
6	UCLA OHRP https://ohrpp.research.ucla.edu/
7	[name]
8	
9	3.4. Phase of Development
10	Phase I/II efficacy and safety trial
11	
12	3.5. Objectives:
13	
14	We propose the use of Mito-MES as drug (FDA IND status) as a novel therapy for viral
15	infections including RSV and SARS-CoV-2. Our proposed use of Mito-MES can be readily
16	advanced to the clinic. In this project, we will focus on the design of an open label phase I/II
17	efficacy study to test the safety and efficacy of Mito-MES to prevent the development and
18	progression of viral infections including RSV and SARS-CoV-2 after high-risk exposure to a
19	person with suspected viral infection (post exposure prophylaxis study). We focus on post
20	exposure prophylaxis study in adults (see study design) and not acute treatment study, since a
21	post exposure prophylaxis study design may require a much smaller sample size to show
22	efficacy and may be more feasible with current resources compared to an acute treatment

24

23

study.

1 Primary objectives:

2

• To determine the efficacy of the treatment with mito-MES 20 mg daily for up to 14 days to prevent development of any viral infection (Yes/no) in high-risk close household contacts of cases with viral infection

To determine the efficacy of the treatment with mito-MES 20 mg daily for up to 14 days to
 prevent development of severe clinical symptoms of any viral infection in high-risk close
 household contacts of cases with viral infection.

9

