10 Viral infection will be defined clinically based on history obtained by the investigator who is an 11 infectious diseases physician and stringent criteria will be followed. Viral infection will be defined as presence of at least two new onset independent symptoms or signs (fever) of respiratory 12 disease that cannot be attributed to bacterial cause. For example, the combination of coryza 13 14 (runny nose) and sore throat is very characteristic of a viral illness since there is no bacterial 15 "rhinitis". The combination of fever and cough is not specific enough presentation since it can be attributed also to bacterial bronchitis or pneumonia. A study participant with chronic allergies or 16 17 chronic sinusitis or asthma will not be included in the study since they may have chronic runny 18 nose or headache or cough.

19

20 **Primary** measures of efficacy (will be assessed in ALL the study participants):

21

The following **primary** outcomes are based on criteria that can be obtained reliably and consistently for all the study participants (based on history and thermometer).

24

• Development of any symptom of viral infection within 14 days after exposure (YES/No).

1	• Severity of viral illness based on a quantitative score system. Each of the above 14
2	symptoms will be given a score based on severity: 1 for mild, 2 for moderate, 3 for severe.
3	Then a total severity score will be estimated (range of score is 0-42). Common example: a
4	person with mild coryza, sore throat and cough will be given a score of 3.
5	
6	
7	Secondary measures of efficacy (will be assessed in study participants but some endpoints
8	such as diagnostic tests may not be available in all the study participants):
9	
10	The following secondary outcomes are based on either non quantitative criteria (categorical)
11	or criteria that may not be available for all the study participants (for example FDA approved
12	diagnostic tests). The study will not pay for any diagnostic tests. These diagnostic tests for
13	viruses may be available in the setting of real world setting and clinical care of each participant
14	(for example if performed by the participant or ordered by a doctor in the setting of clinical care).
15	
16	
 
Development of new onset fever (T> 100.3 F or 38C) based on documented
 

17	measurements of temperature on a daily basis throughout the duration of the study.

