## Main Parameters of Safety

,	•		
۰.	,		
	/		
4	1		

_	
3	Adverse events (day 7, 14): the proportion of participants exhibiting adverse events of
4	any grade as defined using the established  grading scales for the severity of adverse
5	event, such as the Toxicity Grading Scale for Healthy Adult and Adolescent Volunteers
6	Enrolled in Preventive Vaccine Clinical Trials
7	https://www.fda.gov/media/73679/download).
8	
9	Main Parameters of Efficacy
10	
11	Primary measures of efficacy (will be assessed in ALL the study participants):
12	
13	The following primary outcomes are based on criteria that can be obtained reliably and
14	consistently for all the study participants (based on history and thermometer).
15	
16	• Development of any symptom of viral infection within 14 days after exposure (YES/No).
17	• Severity of viral illness based on a quantitative score system. Each of the above 14
18	symptoms will be given a score based on severity: 1 for mild, 2 for moderate, 3 for severe.
19	Then a total severity score will be estimated (range of score is 0-42). Common example: a
20	person with mild coryza, sore throat and cough will be given a score of 3.
21	
22	
23	Secondary measures of efficacy (will be assessed in study participants but some endpoints
24	such as diagnostic tests may not be available in all the study participants):
25	

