1 The following secondary outcomes are based on **either non guantitative** criteria (categorical) 2 or criteria that may not be available for all the study participants (for example FDA approved diagnostic tests). The study will not pay for any diagnostic tests. These diagnostic tests for 3 viruses may be available in the setting of real world setting and clinical care of each participant 4 5 (for example if performed by the participant or ordered by a doctor in the setting of clinical care). 6 Development of new onset fever (T> 100.3 F or 38C) based on documented 7 8 measurements of temperature on a daily basis throughout the duration of the study. 9 Temperature will be recorded in a diary and recording temperature would be a requirement 10 for study participation. 11 **Duration** of ANY of at least three respiratory/systemic symptom of viral illness in **days** (Symptom 1: fever, Symptom 2: cough, Symptom 3: coryza, Symptom 4: sore throat, 12 Symptom 5: shortness of breath, Symptom 6: chills, Symptom 7: fatigue, Symptom 8: loss 13 of smell or taste, Symptom 9: myalgias, Symptom 10: arthralgias, Symptom 11: headache, 14 Symptom 12: nausea, Symptom 13: vomiting, Symptom 14: diarrhea 15 Confirmation of viral infection based on a FDA approved diagnostic test (for example 16 17 respiratory panel PCR that also detects RSV and influenza or other respiratory viruses, rapid antigen test for SARS-CoV-2, PCR for SARS-CoV-2). 18 Symptomatic viral infection: proportion of participants with fever, cough, or other 19 20 respiratory/systemic symptoms (including but not limited to fatigue, loss of smell or taste, 21 myalgias, arthralgias, shortness of breath, sore throat, headache, chills, coryza, nausea, 22 vomiting, diarrhea). 23 Symptomatic moderate to severe viral infection. Based on established score system a viral illness will be categorized as moderate or severe if the participant grades at least 2 different 24 25 symptoms as "moderate" or "severe".

- Symptomatic PCR confirmed SARS-CoV-2 infection
- 2 Need for oxygen therapy (days)
- Hospitalization: Days of hospitalization attributable to viral disease: The median number of
   days (or partial days) spent admitted to an acute care hospital
- Respiratory failure requiring ventilatory support attributable to viral disease: The median
   number of days (or partial days) requiring (i) non-invasive or (ii) invasive ventilation

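### The second primary objective concerns severe symptoms, but neither primary measure isolates them and the secondary moderate-to-severe category can miss them

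*Combined protocol and SAP*

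**What the plan says.** The title describes "mitoquinone/mitoquinol mesylate as prophylaxis for development of severe viral illness". The second primary objective in section 3.5 is to "prevent development of severe clinical symptoms of any viral infection in high-risk close" household contacts.

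Section 3.5 and Main Parameters of Efficacy give two primary measures:

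- "Development of any symptom of viral infection within 14 days after exposure (YES/No"), which has no severity element.
- A total over 14 symptoms: "symptoms will be given a score based on severity: 1 for mild, 2 for moderate, 3 for severe". "Then a total severity score will be estimated (range of score is 0-42"). No cut-off for severe illness is attached. The worked example is that a "person with mild coryza, sore throat and cough will be given a score of 3".

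The Summary differs: it lists the severity score among the secondary endpoints.

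The only categorical severity endpoint is secondary: an "illness will be categorized as moderate or severe if the participant grades at least 2 different" symptoms at either grade. The other secondary outcomes include days of oxygen therapy, median days of hospitalization, median days of ventilatory support, and mortality as a proportion.

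**The concern.** A primary objective framed around severe symptoms needs a result from which a reader can see how many participants had them. The yes/no measure treats a mild cold and a severe illness alike. The sum rises with severity, but it also rises with the number of mild complaints, so a difference in the sum does not show whether severe symptoms became rarer. The one category that uses grade does not separate severe from moderate, and it can leave out a participant who graded a symptom severe.

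The Power/Sample Size section says that effect sizes from this study will inform larger randomized trials. If the sum is read as a measure of severe illness, those trials could be planned on an effect that this study did not measure.

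**Working it through.** **Inputs.** Weights 1, 2 and 3 for mild, moderate and severe; 14 symptoms; range 0-42; worked example of 3; category rule of at least two symptoms at moderate or severe (all from section 3.5 and Main Parameters of Efficacy). Infection definition of at least two new-onset symptoms or signs (section 3.5). 80 participants (Power/Sample Size).

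**Step 1: the plan's own figures.** 14 × 3 = 42 and 3 × 1 = 3. Both are reproduced.

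**Step 2: what a total says about severe symptoms.** With m mild, o moderate and s severe symptoms, T = m + 2o + 3s and m + o + s ≤ 14.

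- No severe symptom (s = 0): T takes every value from 0 to 14 × 2 = 28.
- At least one severe symptom: T takes every value from 3 to 42.
- Overlap: 3 to 28. Only totals of 0-2 rule out a severe symptom, and only 29-42 guarantee one.

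No practical cut-off on the sum therefore isolates severe symptoms.

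**Step 3: the moderate-to-severe category.**

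| Profile | Total | Symptoms at moderate or above | In category | Any severe |
|---|---|---|---|---|
| 4 mild | 4 × 1 = 4 | 0 | no | no |
| 1 severe + 1 mild | 3 + 1 = 4 | 1 | no | yes |
| 2 moderate | 2 + 2 = 4 | 2 | yes | no |
| 1 severe + 1 moderate | 3 + 2 = 5 | 2 | yes | yes |
| 1 severe + 13 mild (extreme) | 3 + 13 = 16 | 1 | no | yes |

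The first three rows share a total of 4. The only one of them with a severe symptom is outside the category, although it meets the two-symptom count in the infection definition.

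**Step 4: median days of hospitalization or ventilation.** With 80 participants, the median is the mean of the 40th and 41st ordered values. If 39 are affected, 80 − 39 = 41 have zero days, both middle values are 0, and so is the median. It becomes positive only from 40 affected. This assumes the median is taken over all 80. If it is taken only over those affected, it describes length of stay and not how many were affected.

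**Step 5: Table 1.** Table 1 scores smell and taste only 0-2, so its maximum is 12 × 3 + 2 × 2 = 40. If complete loss is not counted as severe, the largest total without a severe item is 12 × 2 + 2 × 2 = 28 and the overlap is still 3-28. If it is counted as severe, the smallest total with a severe item is 2, the largest without one is 12 × 2 + 2 × 1 = 26, and the overlap is 2-26. The conclusion is the same either way.

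**The case against.** Several points on the other side stand.

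- **Severe disease is not unmeasured.** A reader might infer that no endpoint captures severe illness, or that a hospitalized participant would disappear from the results. The documents do not support this: oxygen, hospitalization, ventilation and mortality are listed outcomes, and mortality is a proportion. What remains is that hospitalization and ventilation are summarised in a form that can hide how many were affected.
- **Severe grades are counted.** A severe symptom has three times the weight of a mild one in the sum, and it counts towards the category. The defect is that neither isolates severe symptoms.
- **There is no success claim to make.** A reader might infer that the trial could declare success on severe illness. The statistical section rules out formal hypothesis testing and states no success criterion. The risk lies in interpretation and in planning the next trial.
- **A single severe symptom fails the two-symptom infection definition.** That is why the comparison above uses severe plus mild. Even then, the investigator could attribute a particular pair to a bacterial cause, as the protocol does for fever with cough.
- **The data would allow the tabulation.** Symptoms are graded individually each day, Table 2 has a global item with a severe response, and severity is to be compared among symptomatic participants. But no listed outcome reports severe grades. Time to sustained recovery has no stated threshold and measures recovery.
- **The frequency is unknown.** Nothing in the documents shows how often one severe symptom occurs with the rest mild or absent.
- **Late changes are post hoc.** The Summary is partly in the past tense and 80 participants are stated as enrolled, so replacing a primary measure or rewriting the category in an open-label study would be hard to defend.

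**Conclusion.** The second primary objective and the title concern severe symptoms or illness, and neither primary measure isolates them. Totals from 3 to 28 on the 0-42 scale are uninformative about whether a severe symptom occurred. The moderate-to-severe category excludes one severe plus one mild symptom and includes two moderate ones at the same total. The listed care outcomes partly fill the gap, but the hospitalization and ventilation medians would be 0 with up to 39 of 80 affected, if taken over everyone.

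The first two results follow from the stated scoring rules alone. The third assumes an all-participant denominator of 80. The number of participants misclassified in practice cannot be estimated from the documents. This is a mismatch between objective and outcome that should be corrected. It does not invalidate the sum as a measure of symptom burden.

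**What to change.** Keep both primary measures and the moderate-to-severe category. Add one descriptive outcome matched to the second objective: the count and proportion of participants with at least one symptom graded severe on any day, or any oxygen therapy, hospitalization, ventilatory support or death attributable to viral disease. In reporting it:

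- Show each component separately and state the denominator.
- Show it with and without nausea, vomiting and diarrhea, because the protocol itself names gastrointestinal effects as a tolerability concern and a drug effect could be read as severe viral illness.
- State how the 0-2 smell and taste items count.
- Take the worst grade from the daily diary. The Sessions section also records severity by history on days 0, 1, 7 and 14, so name the source.
- Label the outcome by when it was added.

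Report the sum as overall symptom burden and do not present it as evidence on severe illness.

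The cost is wording and one extra table, with no new data. The downside is that few events are likely in healthy adults aged 18-65. With no events among 80 independent participants, the exact two-sided 95% upper limit would be 1 − 0.025^(1/80) = 4.5%, and wider with household clustering or a smaller denominator. Any statement on severe illness will therefore be modest.

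### The plan gives three incompatible primary outcome lists, and its yes/no primary event is ambiguous against the protocol's own two-symptom definition of viral infection

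*Combined protocol and SAP*

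**What the plan says.** **Objective and definition.** The first primary objective is to "prevent development of any viral infection (Yes/no) in high-risk close household contacts of cases with viral infection". The paragraph after the primary objectives states: "Viral infection will be defined as presence of at least two new onset independent symptoms or signs (fever) of respiratory" disease, with a bacterial cause ruled out. It adds: "The combination of fever and cough is not specific enough presentation".

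**Primary outcomes, in three places.**
- Summary: the primary efficacy measure will "be development of viral illness (YES/NO) throughout the study period". Fever is secondary, and the secondary list ends with duration of "symptom of viral illness in days and severity of viral illness based on a quantitative score system".
- Primary measures of efficacy (under Objectives, and again under Main Parameters of Efficacy): "Development of any symptom of viral infection within 14 days after exposure (YES/No", plus a summed severity score. Fever and duration are secondary.
- Power/Sample Size: the sentence covering all primary endpoints lists fever, duration of symptoms and severity. It has no yes/no item.

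**A neighbouring secondary outcome.** "Symptomatic viral infection: proportion of participants with fever, cough, or other" respiratory or systemic symptoms.

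**Score.** "Then a total severity score will be estimated (range of score is 0-42", from 14 symptoms scored 1 to 3 when present. Table 1 is the daily instrument. Severity scores are also taken by history on days 0, 1, 7 and 14.

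**Day 0.** It is study entry in the Participant timeline table and the day of exposure in Sessions by study staff.

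**Who is analysed.** The paragraph before the exclusion criteria removes participants with a positive SARS-CoV-2 test from the final analysis.

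**The concern.** A reader cannot tell from the documents which outcome is primary, or what counts as an event for the yes/no outcome. Enrollment of 80 is reported as complete and the study is open label. The Data and Safety Monitoring Plan has the investigator evaluate all information collected. In that setting, an unsettled list allows the primary outcome and the event rule to be chosen after results are visible, even without intent.

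Power/Sample Size says the study should yield effect sizes for larger randomized trials. An effect size is usable only if another team can reproduce the outcome behind it.

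**Working it through.** **1. Set the lists side by side.**

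| Place | Yes/no | Severity | Fever | Duration |
|---|---|---|---|---|
| Summary | primary | secondary | secondary | secondary |
| Primary measures (both printings) | primary | primary | secondary | secondary |
| Power/Sample Size | absent | primary | primary | primary |

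The Summary and the Primary measures share only yes/no. The Primary measures and Power/Sample Size share only severity. The Summary and Power/Sample Size share nothing. No outcome is common to all three. A further severity endpoint, time to sustained clinical recovery, appears in the section on symptom severity and in no outcome list.

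**2. Apply the two readings of the yes/no event.**

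| Presentation | Literal: any symptom | Definition above it |
|---|---|---|
| Any one of the 14 listed symptoms alone | event | not an event |
| Coryza and sore throat | event | event (the protocol's own example) |
| Fever and cough only | event | called not specific enough |

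The Summary's wording (viral illness) points to the definition. So does the remark in Power/Sample Size that the score considers at least two symptoms under a physician's definition, though that remark concerns severity. The literal wording points the other way, and it makes the primary outcome nearly a copy of the secondary outcome quoted above. No listed outcome states the definition itself. The nearest is moderate to severe infection. It needs two symptoms graded moderate or severe, of any type, with no bacterial exclusion.

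**3. Window.** Let k be the days from exposure to study entry, and let day 0 be study entry. Diary day D14 is then day 14 + k after exposure. The last diary day inside 14 days after exposure is D(14 - k), so k of the 14 diary days fall outside.
- Treated participants: the mito-MES criteria put exposure 1 to 4 days before entry. With k = 4, the last in-window day is D10 and 4 days fall outside.
- General inclusion criterion 4: exposure within 5 days before entry. With k = 5, the last in-window day is D9 and 5 days fall outside.
- If day 0 is the day of exposure, D1 to D14 match the window and none fall outside.

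**4. Score range.** The plan's figure comes from the numbered list in the secondary outcomes: 14 × 3 = 42. Table 1 has 12 items scored 0-3 and two (smell, taste) scored 0-2: 12 × 3 + 2 × 2 = 36 + 4 = 40. The items differ too. The list has arthralgias and one combined smell-or-taste item, whereas Table 1 has no arthralgias item and separates smell from taste.

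**5. Derivation.** There are daily scores and four visit scores per participant. No rule turns them into one primary value. The analysis section compares severity among symptomatic participants without defining symptomatic, so the ambiguity in step 2 carries into the severity outcome.

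**6. Analysis set.** A participant who develops SARS-CoV-2 infection with a positive test is a failure under objective 1, yet is removed from the final analysis. Neither reading of the yes/no outcome then covers any viral infection.

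No sample-size check applies. The plan gives no alpha, power, effect size or event rate, and 80 was set by resources.

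**The case against.** The strongest reply is that this is an exploratory feasibility study with no formal hypothesis test, so no error rate depends on which outcome is called primary. That stands, and it limits the seriousness of the point.

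A second reply is that the definition is printed just above the outcome, so any symptom of viral infection presupposes it. That is a fair reading. A reader might go further the other way and infer that the outcome flatly departs from the definition. The documents do not support that; they leave the matter open. The analysis section's yes/no split on symptoms does not settle it either, because it is the first step of a severity comparison and not a definition of the primary event.

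Third, the plan says its primary outcomes were chosen because history and a thermometer can supply them for everyone. That supports a broad, participant-reported event. The stricter definition brings in an unblinded judgement about bacterial cause. This is why both versions are needed and neither should simply replace the other.

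Fourth, the list in Power/Sample Size might be illustrative. But it is attached to all the primary endpoints, and two of its three items are secondary everywhere else.

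A reader might also want to put a number on the extra events under the literal reading, or attribute some to gastrointestinal effects of the drug. The documents give no background symptom rates and no gastrointestinal rate at 20 mg, and they exclude known gastrointestinal disease predisposing to nausea. Any such figure would rest on assumption. Drug-caused symptoms would also add events in treated participants and so work against apparent benefit.

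**Conclusion.** The point holds and should be fixed; it does not invalidate the design. Three primary lists have no common member, and the yes/no event has two readings. Day 0 has two meanings, which puts up to 4 of 14 diary days outside the window for treated participants (up to 5 under the general criterion) if day 0 is study entry. The stated score maximum is 42 against 40 for the instrument.

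These findings come from comparing current text. The window figure rests only on the stated entry limits and on reading day 0 as study entry. It would be wrong to infer that a power or type I error statement fails, since the plan makes none. How the fever-and-cough pair sits under the definition also needs no new decision, because the definition already calls it not specific enough.

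**What to change.** 1. Reconcile the Summary, both printings of the Primary measures, and Power/Sample Size to one primary list. Date and disclose the change, because 80 participants are already enrolled. Place the recovery endpoint in the outcome lists or remove it.
2. Tabulate the yes/no outcome side by side as any symptom, as listed, and under the protocol's definition. Show the symptom count separately from the investigator's bacterial attribution.
3. Choose one meaning of day 0 and apply one window to every outcome.
4. Use one item list and one derivation rule for the score, for example the highest daily total in the window. State the range as 0-40 if Table 1 is the instrument. Show severity in all participants as well as in the symptomatic subset, with symptomatic defined by the same event rule.
5. Reconcile the removal of SARS-CoV-2-positive participants with objective 1, and show the yes/no outcome with them included.

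**Cost.** The symptom items are already in the daily diary, so the symptom counts need only tabulation. Bacterial attribution is not a diary item and may need retrospective, unblinded judgement. The stricter version gives fewer events and can miss mild cases. Changing a listed outcome after enrollment carries its own risk, which showing both versions with a dated disclosure keeps visible.
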